### **Expected Outcomes:**

It is expected that all patients will see an improvement in their symptoms relating to PTSD and Trauma. Previous studies into the benefits of PEMF therapy have indicated a significant improvement in both physical and mental health conditions. Whilst we do not expect a complete recovery, we expect to see a marginal improvement from all patients. There is no expectation of any adverse outcomes or reactions to the PEMF therapy, apart from headaches or dizziness. All patients have access to [name] during the clinical trial.

### **Reason For Withdrawal:**

A subject may be discontinued from the clinical trial if:

- They fail to arrive for their scheduled appointment
- They show symptoms of severe mental or physical illness
- They wished to withdraw from the trial
- Screening Failure
- They pose a threat to the Lead Investigator
- They refuse to co-operate with the dissemination of the clinical trial
- Subject death

All patients are free to withdraw from the study at any time, for any reason, specified or unspecified, and without prejudice. Reasonable attempts will be made to ensure the patient stays on the clinical trial, but they shall not be coerced. The reason for withdrawal may be noted for clinical trial purposes but shall remain anonymous. Whilst withdrawal is possible, it should be avoided as much as reasonably possible.

This study may be temporarily or permanently suspended if there is a reasonable cause. Written documentation will be provided for the withdrawal of the study if this case arises. Circumstances that may warrant a termination of the trial include:

- Unacceptable or unexpected risk to the patients or staff
- Insufficient compliance to protocol requirements
- Determination of futility

Studies may resume when deemed appropriate by the Lead Investigator.

### **Clinical Trial Outline**

**Prior to Trial** – Selected patients are required to fill out questionnaire provided to them by NCET.

**Week 1** – All patients receive two hours' worth of PEMF treatment across two separate sessions.

**Week 2** – All patients receive two hours' worth of PEMF treatment across two separate sessions.

**Week 3** – All patients receive two hours' worth of PEMF treatment across two separate sessions.

**Week 4** – All patients are required to fill out questionnaire provided to them by NCET. Dissemination of study and findings published.

Whilst the clinical trial is short in length, the ability for patients to get in contact with NCET is always available. Contact can be maintained between the patient and company regarding their lives after the trial. Information provided by patients after the trial has finished will be considered in the trials' findings.

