## Study Summary

Title	Pulsed ElectroMagnetic Field (PEMF) therapy in Treating Post-Traumatic Stress Disorder (PTSD) & Trauma
Methodology	Single arm observing treatment intervention; no control, no placebo/sham
Study Duration	Estimated duration for the main protocol (the start and end of the treatment programme) is approximately 3 weeks
Study Centre(s)	Private clinic in Bristol, U.K.
Objectives	
Primary Objective: To evaluate the efficacy of Artificial Intelligence (AI) guided software rendering PEMF treatment to treat PTSD & Trauma
 
Secondary Objective: To evaluate the feasibility of AI implementation in drastically reducing the time required to train PEMF therapists, thereby allowing faster adoption of PEMF therapy into mainstream practice through use by other licensed/regulated/trained healthcare professionals such as talking therapists, nurses, doctors, social workers, and carers

Number of Actual Participants	5
Diagnosis and Main Inclusion Criteria	
Inclusion Criteria:
 
 
• Aged 18 or over
 
• Have been diagnosed with PTSD or Trauma
 
• Have been experiencing on-going, continuous symptoms of PTSD or Trauma for at least the past 6 months
 
• Can attend 6 sessions lasting 90 minutes over 3 weeks
 
• Consent and Compliance with all requirements of clinical trial, including dissemination of results, with anonymity of identity provided
 
 
Exclusion Criteria:
 
 
• Under the age of 18 years old
 
• Have not been diagnosed with PTSD or Trauma
 
• Have serious health conditions such as cancer
 
• Unable to attend 6 sessions
 

Study Product, Dose, Route, Regimen	Treatment group will receive 6 sessions, each lasting 1.5 hours of PEMF treatment over the course of 3 weeks through the CE-marked CIO devices

	classified by the U.S. Food & Drug Administration as a Type 11a Medical Device. SCIO devices contain a frequency generator and scanning technology, along with electrode harnesses that connect to the forehead, wrists, and ankles. The devices are controlled by software that is guided by A.I.
Statistical Methodology	Primary Endpoint: Symptoms of PTSD & Trauma are evaluated through a questionnaire, with scale ratings for different symptoms. Symptoms were correlated with information available on the NHS website.

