## **Methods:**

### **Study Design:**

Single-arm study involving five (5) subjects undergoing 6 90-minute sessions of Pulsed Electromagnetic Therapy. All patients received the same treatment. Harnesses were placed on the head, wrists, and ankles of the body to conduct the electromagnetic frequencies. Patients were encouraged to rest and relax whilst the therapy was conducted, as it does not require any tasks by the patient. Patients were required to complete a questionnaire before and after the trial. This questionnaire enquired about the different symptoms related to PTSD and Trauma, and asked patients to rate their symptoms on a scale. These questionnaires would form the foundation of the study's findings, as it would give a clear comparison of symptoms before and after the trial.

All aspects of the trial were exempt from a U.K. ethics committee board review because the trial was a non-invasive method of treatment, did not collect and tissue or fluid samples and the device is CE-marked and had been used in other trials previously approved and published on Clinical Trials.gov. Documents were provided on clinicaltrials.gov as evidence of this exemption.

All patients were from the inclusion criteria, and any patients exhibiting cases from our exclusion list were rejected from the pilot study. Patients were recruited through the National Centre for Electromagnetic Therapy social media pages, including Facebook, Instagram, and [www.ncet.co.uk](http://www.ncet.co.uk).

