## **Reflections and Considerations**

The clinical trial highlights the many benefits of PEMF therapy in treating symptoms related to PTSD and Trauma. All patients felt a significant improvement in their lives and indicated a wish to continue with PEMF therapy after the clinical trial had concluded. It can also be suggested that taking the time out of a daily schedule to attend PEMF therapy allows a patient to relax and rest. This form of meditation can be hypothesised as a beneficial side effect to PEMF therapy.

It should also be noted that patients with previous experience with Cognitive Behavioural Therapy (CBT) were more receptive to treatment, especially within the first two sessions. This is due to the selected patients (two of the five patients in the study) being able to communicate their triggers and emotions more clearly to the Lead Practitioner during PEMF treatment. This allowed the patients to experience a form of CBT with the clinical trial staff, whilst providing them time to relax out of their regular schedule. These two patients especially saw an improvement with sleeping, indicating that the opportunity to vocalise their symptoms and emotions helped them alleviate PTSD-related problems.

Whilst the clinical trial was a success in achieving the primary objective, there are numerous considerations and reflections for further clinical trials into PEMF therapy.

- A larger study would be beneficial in further analysing the benefits of PEMF therapy in treating PTSD and Trauma. Access to a larger cohort of volunteers, with a larger time frame of more PEMF sessions would produce a larger result pool. This would also allow for a control group, a treatment group, and a sham group to compare results more accurately and draw wider conclusions to the specific benefits of PEMF treatment.
- Twice weekly sessions proved to be tiring for patients (see Patient Three's statement above), therefore a longer, more spaced-out study would allow patients to recover from PEMF treatment before their subsequent sessions. This would remove the risk of exhausting the patients which may hamper accurate results of the study.
- This study was restricted due to financial and time restraints. Staff numbers were restricted to the Lead Practitioner and a Research Assistant to disseminate results. The financial impact of conducting a clinical trial for free dictated that the trial would be short to make it viable for the sponsor's funding.

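### All efficacy ratings are unblinded self-reports on the treating provider's own form, with no shielded collection described, so courtesy and expectation bias are uncontrolled risks of unknown size

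*Combined protocol and SAP*

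**What the plan says.** The Study Summary describes the design as "Single arm observing treatment intervention; no control, no placebo/sham" and gives the primary endpoint as follows: "Symptoms of PTSD & Trauma are evaluated through a questionnaire, with scale ratings for different symptoms". Study Design confirms that the rater is the patient: the questionnaire "asked patients to rate their symptoms on a scale", and it is named as the basis of the findings.

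The Clinical Trial Outline has the provider issue the form before treatment and again in week 4, where it says "All patients are required to fill out questionnaire provided to them by NCET". It adds that information patients give after the trial will also be considered in the findings. On recruitment, Study Design says "Patients were recruited through the National Centre for Electromagnetic Therapy social media pages", and its list of channels includes the provider's website.

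Reflections and Considerations says the trial was conducted for free, which I read as no charge to patients. On staffing it says "Staff numbers were restricted to the Lead Practitioner and a Research Assistant to disseminate results". During The Trial records that patients also gave verbal feedback to the Lead Practitioner in sessions.

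The text available names no independent assessor and does not say whether forms were named or coded, or who received them. Anonymity is mentioned in the Study Summary, but in connection with dissemination of results.

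**The concern.** Each patient is asked by the organisation that treated them, without charge, whether its treatment worked. Two biases can follow. Courtesy bias is a wish to give the provider a good answer. Expectation bias is a real or perceived change in rating that comes from believing in the therapy. Both would usually raise the after-trial form relative to the baseline form, and a single-arm comparison has nothing to subtract them with.

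The setting makes both plausible. Expected Outcomes anticipates improvement in every patient. Prior to the Trial reports dissatisfaction with earlier medication and therapy. Reflections and Considerations reports that patients confided in the Lead Practitioner during sessions and that all wished to continue.

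What is at stake is the closing statement before the Endnotes. It presents the therapy as a beneficial alternative to prescription medication, and its only caveat is that the results may not represent the whole U.K. That caveat covers neither how patients were recruited nor who collected their ratings.

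**Working it through.** **Inputs.** Before-trial means come from the table in Prior to the Trial and after-trial means from the table in After The Trial, each over five patients. The scale runs from 1 (very severe) to 10 (symptom absent). Higher is taken as better on the quality-of-life, happiness and satisfaction items too, as the sponsor treats them.

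**Step 1: reproduce the stated changes.** Change = after mean − before mean.

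**Step 2: illustrative shift.** The documents give no size for reporting bias, so I assume a uniform upward shift *b* at follow-up and compute residual = change − *b*.

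| Item | Before | After | Change | Less 1 | Less 2 |
|---|---|---|---|---|---|
| Quality of life | 6.0 | 8.0 | 2.0 | 1.0 | 0.0 |
| Depression | 6.4 | 6.4 | 0.0 | −1.0 | −2.0 |
| Falling asleep | 5.6 | 8.2 | 2.6 | 1.6 | 0.6 |
| Flashbacks | 5.0 | 7.4 | 2.4 | 1.4 | 0.4 |
| Headaches or brain fog | 4.6 | 6.0 | 1.4 | 0.4 | −0.6 |
| Fatigue | 5.0 | 6.8 | 1.8 | 0.8 | −0.2 |
| Anger | 4.8 | 7.4 | 2.6 | 1.6 | 0.6 |
| Daily tasks | 5.8 | 7.4 | 1.6 | 0.6 | −0.4 |
| Anxiety | 6.2 | 7.0 | 0.8 | −0.2 | −1.2 |
| Happiness | 6.2 | 8.2 | 2.0 | 1.0 | 0.0 |
| Satisfaction | 5.8 | 7.8 | 2.0 | 1.0 | 0.0 |
| **Mean** | | | **1.75** | **0.75** | **−0.25** |

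All eleven stated changes reproduce. They sum to 19.2, so the mean change is 19.2 / 11 = 1.75 points (equivalently 96 points over 55 ratings).

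- *b* = 1: nine of eleven items stay above zero.
- *b* = 1.5: the mean residual is 0.25 and eight items stay above zero.
- *b* = 2: only falling asleep, anger and flashbacks stay above zero.
- *b* = 3: no item stays above zero.
- Break-even for the overall mean: *b* = 1.75.

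**Step 3: what shielded collection could remove.** Let the total bias be *B* and the courtesy share *f*, and suppose, generously, that coding and shielding remove all courtesy bias. What remains is *B*(1 − *f*).

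| *B* | *f* = 0 | *f* = 0.5 | *f* = 1 |
|---|---|---|---|
| 1 point | 1.0 | 0.5 | 0 |
| 2 points | 2.0 | 1.0 | 0 |

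The documents fix neither *B* nor *f*. The expectation part stays in full whatever is done with the forms.

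**The case against.** The strongest reply is that none of this shows bias occurred. Depression stayed at 6.4, which a uniform upward shift would not produce unless true depression had worsened by the same amount. The 1- and 2-point shifts have no source in the documents. This stands: the figures are a sensitivity range, not an estimate.

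A reader might also draw stronger inferences that the documents do not support:

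- **That the patients were followers or earlier clients.** Study Design names pages and a website as recruitment channels. It says nothing of prior following or treatment, so there is no shown problem for an exclusion of earlier clients to solve.
- **That staff linked forms to patients.** Reflections and Considerations says of the two patients with CBT experience that "These two patients especially saw an improvement with sleeping". That remark could rest on the verbal feedback given in sessions.
- **That forms were filled in under the eyes of staff.** After The Trial says the baseline questionnaire was sent out, so completion away from the clinic may already have been the practice.

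The sponsor can add that Reflections and Considerations already names a control group and a sham group for a larger study, and that resting during sessions may itself help. That is fair, and a sham group is the right answer to expectation. It leaves form handling untouched, and the closing conclusion makes no allowance for either bias.

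Finally, with five patients and two staff a code gives weak anonymity, and the Research Assistant belongs to the provider's team. This also stands and limits what the fix can promise.

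**Conclusion.** The concern holds as an uncontrolled risk, not as a demonstrated bias. Every efficacy rating is an unblinded self-report on the provider's form, from patients recruited through its own channels, with no coded or shielded collection described and no comparator. It would go too far to say that bias entered every result, or that a coded form would deal with expectation.

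The size is unknown. If the shift were uniform across items, about 1.75 points would account for the whole mean change, and 2 points would leave three of eleven items above zero. Both figures rest on that uniformity assumption, which the unchanged depression score does not support but cannot exclude. The point concerns efficacy ratings only; attendance, for example, is not a self-rating.

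The practical consequence is that the reported changes cannot be attributed to the therapy as the closing statement does.

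**What to change.** **Now, in the closing statement.** Remove the claim that the therapy is shown to be a beneficial alternative to medication. Suggested replacement: *Five patients recruited through the provider's own pages and website reported mean changes of 0 to 2.6 points on eleven self-rated items. The ratings were unblinded and uncontrolled, and the study cannot separate these changes from reporting bias or expectation.* The cost is an edit.

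**In the follow-on study, in the section corresponding to the Clinical Trial Outline** (results here are already reported, so collection cannot be changed for this trial):

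- Identify both forms by a code that links each patient's before and after answers, and state that they are completed away from the clinic.
- Have them returned to someone other than the Lead Practitioner. The Research Assistant is workable if the weak anonymity is acknowledged; a recipient outside the treating team would be stronger.
- Withhold the forms from the Lead Practitioner until all are in, and say so on the form so that patients know it when they answer.
- Add two baseline questions, on earlier PEMF use and on expected benefit, reported descriptively.
- State that these steps limit courtesy bias only, and that expectation bias needs a comparator such as the sham group the sponsor already mentions.

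Using the Research Assistant, the collection changes need two questions, one sentence on the form and a different route for the paperwork, with no extra staff. An outside recipient or a sham arm would cost more.

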## Results & Findings

### **Prior to the Trial**

Once participants had been screened and approved for clinical trial study, they were required to fill out a questionnaire that sought to establish the specific issues that they were experiencing due to PTSD and Trauma. These responses were weighted as an average and are provided below.

For clarification, a rating of one (1) on the scale indicates a very severe case of a specific symptom, five (5) means a frequent feeling of a symptom, and ten (10) indicates that the symptom is not experienced at all. A weighted average score has been chosen as a foundation for our results, to compare them more accurately before and after the trial. However, specific notes and observations shall be included where needed.

Statements were also used, whereupon a patient would respond with either Daily (3 or more times a week), Weekly (2 to 3 times a week), Monthly (3 to 4 times a month), or Rarely (Once every 3 months or longer).

Question	Average Score
Have you experienced or witnessed a life-changing event that caused intense fear, hopelessness or horror?	All patients recorded 'Yes'.
Have you experienced either repeating dreams, flashbacks, or intense physical/emotional stress that relate back to the	Daily – 1 Patient Monthly – 2 Patients Rarely – 2 Patients

traumatic event(s)?	
Do you avoid thoughts, feelings, actions, conversations, or people related to the event?	Daily – 1 Patient Weekly – 2 Patients Monthly – 1 Patient Rarely – 1 Patient
Have you felt detached or negative towards yourself or others since the traumatic event(s) happened?	Daily – 4 Patients Monthly – 1 Patient
Do you have problems sleeping?	Daily – 1 Patient Weekly – 2 Patients Rarely – 2 Patients
Do you become increasingly irritable, angry, or engage in self-destructive behaviour?	Daily – 1 Patient Monthly – 3 Patients Rarely – 1 Patient
How long have your symptoms persisted?	Longer Than Three Years – 3 Patients Longer Than A Year – 1 Patient 8-12 Months – 1 Patient
Do you experience heightened version of anxiety, sensitivity, or depression?	Daily – 3 Patients Weekly – 1 Patient Monthly – 1 Patient
Rate Your Quality of Life	Average Score: 6
Rate The Severity of Depression	Average Score: 6.4
Rate How Difficult It Is To Fall Asleep	Average Score: 5.6
Rate The Severity of Flashbacks Relating to a Traumatic Event	Average Score: 5
Rate The Severity of Headaches or 'Brain Fog'	Average Score: 4.6
Rate The Severity of Fatigue	Average Score: 5
Rate The Severity of Anger or Irritable Outbursts	Average Score: 4.8
Rate How Difficult It Is To Complete Daily Tasks	Average Score: 5.8
Rate The Severity of Your Anxiety	Average Score: 6.2

Rate Your Level of Overall Happiness	Average Score: 6.2
Rate Your Level of Satisfaction and Fulfilment In Life	Average Score: 5.8

As illustrated in the above table, symptoms varied among the patients. As an overall judgement, all patients were experiencing mild to severe symptoms related to PTSD and Trauma.

It is important to note that three of the patients had received medication for their symptoms prior to the study, but none were currently receiving treatment during the clinical trial. There was an overwhelming consensus that prescription medication from the NHS was not beneficial in helping their symptoms. One patient felt 'failed' by the therapy they had received, whilst others noted that the medication exacerbated symptoms.

Regarding sleeping, the patients were given an option to describe their sleeping situations. All patients reported a problem with sleeping. These causes ranged from harmful internal dialogue and flashbacks to insomnia and difficulty gaining a restful sleep.

These initial results will be used in the 'After Trial Results' section, where the averages will be compared, and conclusion can be drawn. Further observations will be available below the initial results to accord for any individual cases requiring attention, or further clarification on certain results.

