### After The Trial

Once the trial had been completed over the course of 3 weeks, patients were asked to complete the same questionnaire that was sent out prior to the clinical trial. In the table below, responses have been recorded as an average, with a percentage comparison of improvement or decline in symptoms.

Question	Average Score
Have you experienced or witnessed a life-changing event that caused intense fear, hopelessness or horror?	All patients recorded 'Yes'.
Rate Your Quality of Life	Average Score: 8 ( Improvement of >2 points )
Rate The Severity of Depression	Average Score: 6.4 ( No change )
Rate How Difficult It Is To Fall Asleep	Average Score: 8.2 ( Improvement of >2.6 points )
Rate The Severity of Flashbacks Relating to a Traumatic Event	Average Score: 7.4 ( Improvement of >2.4 points )
Rate The Severity of Headaches or 'Brain Fog'	Average Score: 6 ( Improvement of >1.4 points )
Rate The Severity of Fatigue	Average Score: 6.8 ( Improvement of >1.8 points )
Rate The Severity of Anger or Irritable Outbursts	Average Score: 7.4 ( Improvement of >2.6 points )

Rate How Difficult It Is To Complete Daily Tasks	Average Score: 7.4 ( Improvement of >1.6 points )
Rate The Severity of Your Anxiety	Average Score: 7 ( Improvement of >0.8 points )
Rate Your Level of Overall Happiness	Average Score: 8.2 ( Improvement of >2 points )
Rate Your Level of Satisfaction and Fulfilment In Life	Average Score: 7.8 ( Improvement of >2 points )

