## Discussion

Regarding nearly all the symptoms analysed in the clinical trial, there was a mild to significant improvement. The largest improvement of an average of 2.6 points was discovered in symptoms related to insomnia and anger outbursts. It can be hypothesised that due to increased rest and relaxation, patients were able to manage their negative emotions more efficiently.

Positive results were also found within the patients' own value of life. Large improvements were found in a patients' perception of overall happiness, satisfaction and fulfilment, as well as general quality of life. All these values increased by a score of 2 or more on average. It is evident that the PEMF treatment is beneficial in providing patients with a relaxing and calm therapy which in turn helps appreciation for quality of life, and motivation in facing daily tasks head on.

Physical symptoms were also improved using PEMF therapy. Issues relating to headaches, fatigue, and flashbacks were all reduced over the course of the trial. Patients reported feeling more relaxed, and physical pains has subsided (See 'Patient Four' below).

It is important to note that the only symptom that experienced no average change was depression. It can be postulated that this is due to depression being a more deep-rooted issue which was prevalent for an extended period prior to the clinical trial. It is promising to see that cases of depression were not worsened during the trial, indicating that PEMF therapy is able to improve symptoms related to depression (fatigue, insomnia, anger). Nonetheless, the lack of change in depression forms a consideration for future clinical trials (see 'Considerations').

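### The averages reported after the trial do not show that symptoms improved in every patient or that nobody worsened, and the repeated frequency questions are not reported

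*Combined protocol and SAP*

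**What the plan says.** The Study Summary makes a symptom questionnaire the primary endpoint. The Study Design section calls it the basis of the findings, on the ground that "it would give a clear comparison of symptoms before and after the trial".

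**Scale.** Under Prior to the Trial, "a rating of one (1) on the scale indicates a very severe case of a specific symptom, five (5) means a frequent feeling" and "ten (10) indicates that the symptom is not experienced at all". Eight items are worded as severity or difficulty, for example "Rate The Severity of Your Anxiety". Three more cover quality of life, happiness and satisfaction. All eleven are reported as averages.

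**Frequency answers.** Six baseline questions use categories, of which the first two are defined as "Daily (3 or more times a week), Weekly (2 to 3 times a week". They cover flashbacks or dreams, avoidance, detachment, sleep, irritability, and heightened anxiety or depression. Baseline counts are given for each.

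**After the trial.** The document states that "patients were asked to complete the same questionnaire that was sent out prior to the clinical trial". The table that follows contains the yes/no question on a life-changing event and the eleven averages, and nothing else.

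**Conclusions.** The Discussion notes that "the only symptom that experienced no average change was depression", and adds: "It is promising to see that cases of depression were not worsened during the trial". The closing conclusion, after Reflections and Considerations, says that almost all symptoms improved in all patients and that no worsening was recorded. It goes on to present the therapy as a beneficial alternative to prescription medication.

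**The concern.** An average over five patients describes the group. It does not say how many patients went up, stayed the same or went down. A statement that everyone improved, or that nobody worsened, needs each patient's two ratings side by side, and the results tables do not give them.

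This matters because the trial has no control group and no planned test. The claim of consistent benefit in every patient therefore carries much of the weight in the closing argument that the primary objective was met. If the record supports only a rise in group means, the conclusion is noticeably weaker.

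The missing frequency answers add to this. They are the one other description of several of the same symptoms, and a repeat of the same form should have produced them.

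**Working it through.** **Inputs.** Five patients (Study Design); baseline means (Prior to the Trial); after-trial means (After The Trial).

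**Step 1: reproduce the stated changes.** Change = after minus before; total = 5 × mean.

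| Symptom item | Before | After | Change | Total before → after | Total gain |
|---|---|---|---|---|---|
| Depression | 6.4 | 6.4 | 0 | 32 → 32 | 0 |
| Falling asleep | 5.6 | 8.2 | 2.6 | 28 → 41 | 13 |
| Flashbacks | 5 | 7.4 | 2.4 | 25 → 37 | 12 |
| Headaches or brain fog | 4.6 | 6 | 1.4 | 23 → 30 | 7 |
| Fatigue | 5 | 6.8 | 1.8 | 25 → 34 | 9 |
| Anger | 4.8 | 7.4 | 2.6 | 24 → 37 | 13 |
| Daily tasks | 5.8 | 7.4 | 1.6 | 29 → 37 | 8 |
| Anxiety | 6.2 | 7 | 0.8 | 31 → 35 | 4 |

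The three well-being items each rise by 2.0 (6 to 8, 6.2 to 8.2, 5.8 to 7.8). Every stated change is reproduced. Each equals the printed figure, so the greater-than signs in the table are not needed. Over the eight symptom items the total gain is 66, and 66 / 40 = 1.65.

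**Step 2: are these plain means of whole numbers?** The document calls the averages weighted but gives no weights. All 22 reported means are multiples of 0.2, which is what plain means of five whole numbers give. The steps below assume this, with ratings from 1 to 10.

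**Step 3: anxiety.** If all five patients improved, each gained at least 1 point, so the total gain would be at least 5 × 1 = 5. The total gain is 4. At most four patients improved.

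**Step 4: depression.** The five changes add to 32 − 32 = 0. Either all five are zero, or at least one is positive and at least one negative. The Discussion's remark, read as a statement about patients, is true only in the first case.

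**Step 5: the other six symptom items.** Their total gains run from 7 to 13, so five improvements are possible but not implied. For headaches, changes of +2, +2, +1, +1, +1 add to 7, and so do +3, +2, +2, +1, −1. The reported mean of 1.4 cannot tell these apart.

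The outer limit is three patients falling. With four falling by at least 1, the fifth could rise by at most 9, giving 9 − 4 = 5, which is below 7. Three is attainable: for sleep, (1, 1, 8, 9, 9) to (10, 10, 7, 7, 7) gives 28 and 41. That pattern is extreme. The two risers must gain at least 13 + 3 = 16 of a possible 18 points. It is an arithmetic bound, not an estimate.

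**Step 6: frequency questions.** Six are tabulated at baseline (illustrations 1.1 to 1.5 and 1.8). None appears in the After The Trial table, and none appears among the titles of illustrations 2.1 to 2.11. The life-changing-event question does reappear in the table, so the table was not restricted to ratings.

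**The case against.** **The wording is qualified.** The closing sentence speaks of almost all symptoms, which may exempt anxiety and depression. The Discussion's remark on depression comes straight after the statement on the average and can be read at group level. Both readings are fair, so the arithmetic does not prove the closing sentence false. What stands is that the averages do not establish it for the remaining six symptom items either, and that a reader will take both remarks as statements about patients.

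**Other evidence may exist.** The document refers to individual patient statements and reports verbal feedback from each patient. Some pages and nearly all charts were not available to this review. The trial record may therefore support more than the tables do. Even so, felt benefit and willingness to continue are not item-level ratings.

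**The frequency answers are a weak check.** Daily and Weekly both include three times a week. Monthly, and Rarely (once every three months or longer), can barely register change over a three-week programme. Several questions have no clear recent time window. No frequency question covers headaches, fatigue or daily tasks. All of this stands, and it limits the answers to a supporting role. It does not explain why they are missing from a form described as the same.

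**Stronger readings that a reader might infer.** One is that some patients did get worse. The documents do not show that: for depression no change in anyone is possible, and for anxiety the certain result is only that at least one patient did not improve. Another is that patients read the severity items backwards, so that the gains are an artefact. The document states the anchors at 1, 5 and 10 and applies them consistently, the three well-being means also rose, and nothing in the text indicates a reversed answer. What remains is a minor query: the available text does not show whether patients saw those anchors on the form.

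**Conclusion.** The statements about every patient are not supported by the results as reported. What the tables do show is that, on the stated scale, seven of eight symptom means rose, the depression mean did not change, and the three well-being means each rose by 2.0.

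Improvement in all five patients is ruled out for anxiety. For depression it is ruled out too, since a total change of zero cannot come from five gains. It is undetermined for the other six symptom items. Absence of worsening in depression holds only if no patient's rating changed.

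The depression result needs only that the averages are plain means. The anxiety result also needs whole-number ratings: with half-point steps, five gains of 0.5 would total 2.5, which is below 4. The pattern of the 22 means favours both assumptions but does not prove them.

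Separately, either the six frequency questions were repeated and not reported in the table, or the second form was not the same. The text needs correcting in either case. Both points are reporting faults that should be fixed because they change what the trial can conclude. The query about anchors is minor.

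**What to change.** 1. Add a de-identified table of the five paired ratings for each item, with the eight symptom items separate from the three well-being items. State whether the averages are weighted and, if so, how.
2. Report the after-trial answers to the six frequency questions as counts per category beside the baseline counts. If they were not collected, say so and correct the description of the second questionnaire. Treat them as supportive only.
3. Unless the paired data support more, limit the closing conclusion to: on the stated scale, mean ratings rose on 7 of 8 symptom items and did not change for depression. Limit the Discussion to: the mean depression rating did not change.
4. Minor: confirm from the five completed forms which anchors patients saw on the severity and difficulty items.

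**Cost.** A check of five existing forms, one small table and a few edited sentences; no new data. The conclusion may become less favourable, and with five patients the table must be laid out so that nobody can be identified, for example by not linking rows to the individual patient statements.
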